#### **3.4.8 Dynamometry**

Dynamometry measures the static muscle strength without any movement. Manual dynamometry with hand-held devices and quantitative myometry testing (QMT) with bedframe equipment will be used to assess the skeletal muscle strength of study subjects in both the upper and lower limbs bilaterally. Manual dynamometry be assessed at Screening, Week 4, Week 14, Week 24, Week 48, and End of Treatment (Week 60). QMT will be assessed at Screening, Week 4, and End of Treatment (Week 60).

Descriptive statistics for percent predicted QMT as well as change from baseline will be presented for: (a.) all muscles combined; (b.) upper extremity strength, which includes the hands, shoulders and elbows combined; and (c.) lower extremity strength, which includes knee extension, knee flexion, and ankle dorsiflexors combined. Percent predicted QMT scores will be calculated using SAS® code provided in [Appendix 9](#) (with additional extremity details in [Appendix 10](#)).

Descriptive statistics for total manual dynamometry as well as change from baseline will be presented for: (a.) all muscles combined; (b.) upper extremity strength, which includes the hands, shoulders and elbows combined; and (c.) lower extremity strength, which includes right and left ankle dorsiflexors combined. Raw scores will be presented.

Descriptive statistics of manual dynamometry average and maximum weight in kilogram per visit as well as the change from baseline and percent change from baseline will be presented according to assessment (dominant shoulder abductors, non-dominant shoulder abductors, dominant elbow flexors, non-dominant elbow flexors, dominant elbow

extensors, non-dominant elbow extensors, dominant hand grip, non-dominant hand grip, right ankle dorsiflexors, and left ankle dorsiflexors). Raw scores will be presented.

Descriptive statistics of normalized manual dynamometry average and maximum weight in kilogram per visit as well as the change from baseline will be presented by overall upper extremity and according to assessment (dominant shoulder abductors, non-dominant shoulder abductors, dominant elbow flexors, non-dominant elbow flexors, dominant elbow extensors, non-dominant elbow extensors, dominant hand grip, and non-dominant hand grip).

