### Longitudinal analysis

For longitudinal analysis of disease progression, we only want to include muscles that have category 'B' at baseline – the rationale being that inclusion of Normal appearing muscles (likely not affected by disease) or End-stage appearing muscles (likely not much function left) would only add noise and uncertainty to the analysis of longitudinal changes. Hence:

- If the muscle category is A, C or NA at baseline, the muscle should not be included in longitudinal analysis.
- If the muscle category is B at baseline, the muscle should be included in longitudinal analysis.

We include quality control SI parameters from both timepoints to ensure that we remove a muscle from the calculation if it's unanalyzable in any or both timepoints. For cleaner equations, we combine the statistical

inclusion parameters for the two timepoints here:

$$SI_{long}^{comb} = SI_{long, tp1} \cdot SI_{long, tp2}$$

The absolute change in total LMV, MFI and MFF between timepoint 1 (tp1) and timepoint 2 (tp2) becomes:

$$\begin{aligned}\Delta LMV_{tot} &= \sum_{i \in SI_{cat, tp1=B}} SI_{long, i}^{comb} \cdot (LMV_{i, tp2} - LMV_{i, tp1}) \\ \Delta MFI_{tot} &= \frac{\sum_{i \in SI_{cat, tp1=B}} SI_{long, i}^{comb} \cdot MFI_{i, tp2} \cdot LMV_{i, tp2}}{\sum_{i \in SI_{cat, tp1=B}} SI_{long, i}^{comb} \cdot LMV_{i, tp2}} - \frac{\sum_{i \in SI_{cat, tp1=B}} SI_{long, i}^{comb} \cdot MFI_{i, tp1} \cdot LMV_{i, tp1}}{\sum_{i \in SI_{cat, tp1=B}} SI_{long, i}^{comb} \cdot LMV_{i, tp1}} \\ \Delta MFF_{tot} &= \left( 1 - \frac{\sum_{i \in SI_{cat, tp1=B}} SI_{long, i}^{comb} \cdot LMV_{i, tp2}}{\sum_{i \in SI_{cat, tp1=B}} SI_{long, i}^{comb} \cdot TMV_{i, tp2}} \right) - \left( 1 - \frac{\sum_{i \in SI_{cat, tp1=B}} SI_{long, i}^{comb} \cdot LMV_{i, tp1}}{\sum_{i \in SI_{cat, tp1=B}} SI_{long, i}^{comb} \cdot TMV_{i, tp1}} \right)\end{aligned}$$

The reason we only include the muscle category parameter from timepoint 1 is that we want to make sure to follow a muscle that is 'Affected' at baseline/tp1, even if it progressed into 'End-stage' at follow-up/tp2. A subject with no analyzable muscles should not be included in longitudinal analysis (this can be ensured by removing any subjects with total LMV = 0).

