Test='KFR'; MedMax=9.8*KFR; output;

Test='KEL'; MedMax=9.8*KEL; output;
Test='KER'; MedMax=9.8*KER; output;

Test='HGL'; MedMax=HGL; output;*hand grip stays in kg;
Test='HGR'; MedMax=HGR; output;

keep record_id redcap_event_name  sex age height  test medmax  ;
run;
*proc print; run;
```

\*creates percent and standardized scores;

```
data qma3; set qma2;
%include 'n:\research\FSH\qmt_stan_updated.sas';
%include 'n:\research\ibm\predict.sas';
predict2=2.71828**predict;
if test='SBL' OR TEST='SBR' OR TEST='EFL' OR TEST='EFR' OR TEST='EEL' OR TEST='EER' or
test='DFL' OR TEST='DFR'
OR TEST='KFL' OR TEST='KFR' OR TEST='KER' OR TEST='KEL' or test='DFL' or test='DFR'
THEN Percent=(medmax/predict2)*100;
if test='HGR' or test='HGL' then percent=(medmax/predict)*100;
logmm=log (medmax+1);run;
```

```
proc sort data=qma3;by record_id redcap_event_name ;run;
proc means data=qma3 nopol; by record_id redcap_event_name ;
var stanqmt percent age;
output out=qmameans mean=;
label stanqmt='Standartized Overall QMT Score(SA, EF, EE, AD,KF,KE,HG)';
label percent='QMT:Overall Percent Predicted(SA, EF, EE, AD,KF,KE,HG) ';
run;
```

\*Below codes calculates Lower Extremity QMA standardized and percent scores;

```
data qma2u; set qma;
Test='SBL'; MedMax=9.8*SAL; output; ****;
Test='SBR'; MedMax=9.8*SAR; output; ****;

Test='EFL'; MedMax=9.8*EFL; output;
Test='EFR'; MedMax=9.8*EFR; output;

Test='EEL'; MedMax=9.8*EEL; output;
Test='EER'; MedMax=9.8*EER; output;
```

```
Test='HGL'; MedMax=HGL; output;
Test='HGR'; MedMax=HGR; output;

keep record_id redcap_event_name sex age height test
medmax ;
run;

data qma3u; set qma2u;
%include 'n:\research\FSH\qmt_stan_updated.sas';
%include 'n:\research\ibm\predict.sas';
predict2=2.71828**predict;
if test='SBL' OR TEST='SBR' OR TEST='EFL' OR TEST='EFR' OR TEST='EEL' OR TEST='EER' THEN ;
Percent_upper=(medmax/predict2)*100;
if test='HGR' or test='HGL' then percent_upper=(medmax/predict)*100;
logmm=log(medmax+1);
run;

data qma3u;set qma3u(rename=(stanqmt=stanqmt_upper));
run;

proc sort data=qma3u;by record_id redcap_event_name ; ;run;
proc means data=qma3u noprint; by record_id redcap_event_name ;
var stanqmt_upper percent_upper age;
output out=qmameans_upper mean=;
run;
data qmameans_upper;set qmameans_upper;
label stanqmt_upper='Standardized Upper Extremity QMT Score(SA,EF,EE,HG)';
label percent_upper=' Upper Extremity Percent Predicted QMT Score(SA,EF,EE,HG)';run;

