*Below codes calculates Lower Extremity QMA standardized and percent scores;
data qma2l; set qma;

Test='DFL'; MedMax=9.8*ADL; output; ****;
Test='DFR'; MedMax=9.8*ADR; output; ****;

Test='KFL'; MedMax=9.8*KFL; output;
```

```
Test='KFR'; MedMax=9.8*KFR; output;

Test='KEL'; MedMax=9.8*KEL; output;
Test='KER'; MedMax=9.8*KER; output;

keep record_id redcap_event_name sex age height test
medmax ;
run;

data qma31; set qma21;
%include 'n:\research\FSH\qmt_stan_updated.sas';
%include 'n:\research\ibm\predict.sas';
predict2=2.71828**predict;
Percent_leg=(medmax/predict2)*100;
logmm=log (medmax+1);run;

data qma31;set qma31(rename=(stanqmt=stanqmt_leg));
run;

proc sort data=qma31;by record_id redcap_event_name date40; ;run;
proc means data=qma31 noprint; by record_id redcap_event_name ;
  var stanqmt_leg percent_leg age;
  output out=qmameans_leg mean=;
run;
data qmameans_leg;set qmameans_leg;
label stanqmt_leg='Standardized Lower Extremity QMT Score(AD, KF, KE)';
label percent_leg='Lower Extremity Percent Predicted QMT Score(AD, KF, KE)';run;

*Merge the original qmt enties , overall qma , lower and upper qma means;

data
merge qmt qmameans qmameans_upper qmameans_leg;by record_id redcap_event_name ;run;
```

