**Over all QMT is estimated from ( SA, EF, EE, AD,KF,KE,HG):**

**HG(Hand Grip):**

55 hglmvict Num 8 BEST12. BEST32. HGL (Hand Grip-Left) QMT (kg)  
**56** hgrmvict Num 8 BEST12. BEST32. HGR (Hand Grip-Right) QMT (kg)

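### The QMT composites average whichever tests have a value at each visit, so change from baseline can compare different sets of muscles

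*SAP*

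**What the plan says.** SAP 3.4.8 makes the composites and their change from baseline a planned output: "Descriptive statistics for percent predicted QMT as well as change from baseline will be presented for: (a.) all muscles combined", and likewise for the upper and lower extremities. QMT is scheduled at Screening, Week 4 and Week 60.

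Appendix 9 gives the scoring code. Each test is turned into a percentage of its predicted value ("THEN Percent=(medmax/predict2)*100" for all tests except hand grip, which is handled the same way without the exponential). PROC MEANS then averages the percentages within each subject and visit ("by record_id redcap_event_name"). The output step is "output out=qmameans mean" for the overall score, "output out=qmameans_upper mean" for the upper score and "output out=qmameans_leg mean" for the lower score. Appendix 10 names the components: "Over all QMT is estimated from ( SA, EF, EE, AD,KF,KE,HG", seven muscle groups on two sides.

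No QMT rule for a missing test appears elsewhere:

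- SAP 2.3.6 covers adverse event data and the DUX4 score only.
- Protocol 10.1.1 asks that a subject have a baseline and a follow-up value, which a composite built from fewer tests satisfies.
- SAP 3.6 repeats the hand-held dynamometry analysis with an averaged baseline, but not QMT.
- Protocol 8.2 leaves the dynamometry procedure to a separate manual, so the documents do not say whether a muscle too weak to test is left blank or entered as 0.

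**The concern.** A missing measurement gives a missing percentage, and PROC MEANS divides by the number of tests present. Nothing ties the tests averaged at Week 60 to those averaged at baseline. When a test is absent at one of the two visits, part of the reported change is simply a change in which muscles were counted.

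The direction matters in this disease. Protocol 1.1 describes muscle involvement as commonly asymmetric, so one test can lie far below a subject's average. If that muscle becomes untestable and the field is left blank, the average rises at the moment the subject has worsened. If the weak muscle is missing at baseline and tested later, the score shows a false decline. SAP 2.3.1 takes the last pre-dose value as baseline, so an incomplete Week 4 composite would replace a complete screening one.

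No later scheduled QMT would expose the problem. SAP 3.4.8 tabulates QMT only as composites, so a lost test would be visible only in the listings.

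**Working it through.** The plan states no QMT figure to reproduce, so the check follows the code's arithmetic.

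**Inputs from the documents**

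- Number of tests: 7 groups × 2 sides = 14 overall; 4 × 2 = 8 upper; 3 × 2 = 6 lower (Appendices 9 and 10).
- Subjects: 14 enrolled (protocol 4.1).
- Natural loss of strength: about 1% to 4% per year (protocol 1.1), read here as relative to current strength.

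**Assumptions, not in the documents:** in one subject the other tests average 60% of predicted and do not change; one muscle at w = 10% (or 20%) is tested at baseline and left blank at Week 60.

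**Formula.** If the other n − 1 tests average m, the baseline score is ((n − 1)m + w)/n and the Week 60 score is m. The false rise is (m − w)/n.

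| Score | n | Baseline, w = 10% | Week 60 | False rise | False rise, w = 20% | Group mean, 1 of 14 (w = 10%) |
|---|---|---|---|---|---|---|
| Overall | 14 | (13×60 + 10)/14 = 56.43 | 60 | +3.57 | +2.86 | 3.57/14 = +0.26 |
| Upper | 8 | (7×60 + 10)/8 = 53.75 | 60 | +6.25 | +5.00 | 6.25/14 = +0.45 |
| Lower | 6 | (5×60 + 10)/6 = 51.67 | 60 | +8.33 | +6.67 | 8.33/14 = +0.60 |

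A 1% to 4% loss at 60% of predicted is 0.6 to 2.4 points. Every false rise in the table exceeds that for the affected subject. The group shift for the lower score (0.60) is about the size of a 1% loss; the other two group shifts are smaller.

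**A second case with real decline.** Take 13 tests at 50% and one at 10%, with every muscle declining by 1% or 4%. The baseline overall score is (13×50 + 10)/14 = 47.14.

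| Treatment of the weak muscle at Week 60 | 1% decline | 4% decline |
|---|---|---|
| Still tested | 46.67 (−0.47) | 45.26 (−1.89) |
| Blank, code as written | 49.5 (+2.36) | 48.0 (+0.86) |
| Blank, matched tests (baseline 50.0) | 49.5 (−0.50) | 48.0 (−2.00) |
| Entered as 0 | 13×49.5/14 = 45.96 (−1.18) | 13×48/14 = 44.57 (−2.57) |

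The code as written reports a rise although every tested muscle fell. Matching removes the false rise but leaves out the lost muscle's own decline; the zero score includes it.

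**How many subjects would mask a group decline.** If unaffected subjects change by −0.5 (or −2.0) and affected ones by +2.36 (or +0.86), k affected subjects out of 14 bring the overall group mean to zero when k = 14×0.5/2.86 = 2.4, so about 3 (1% decline), or k = 14×2.0/2.86 = 9.8, so about 10 (4% decline).

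**Opposite direction.** With 13 tests at 50% and a muscle at 90% missing at Week 60, the overall score falls from (650 + 90)/14 = 52.86 to 50.0, a false loss of 2.86 points.

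**The case against.** The strongest objection is that the upward bias depends on a data convention the documents do not show. The code accepts zeros: the percentage formula handles them, and the standardised score adds 1 before taking logs. If the separate manual has an untestable muscle entered as 0, the score falls as it should. This stands as a condition on the direction of bias. It does not supply a rule for tests missing for other reasons.

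A reader might infer that the composite hides progression in this trial. The documents do not support that. They do not show that any test was missing, users of wheelchairs or walkers were excluded, and one affected subject moves the group mean only by the fractions of a point shown in the working.

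A reader might also take the MRI composites as a precedent for handling weakness. Appendix 6 does combine both timepoints to "remove a muscle from the calculation if it's unanalyzable in any or both timepoints", which supports comparing like with like. But that exclusion concerns signal quality, and the same section deliberately follows an affected muscle that becomes end-stage. It offers no model for dropping a muscle because it became too weak.

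Nor does the upward bias carry over automatically to the hand-held combined totals. SAP 3.4.8 gives no formula for them, and a sum would fall when a test is missing. Hand-held results are also tabulated muscle by muscle and at visits before Week 60, which is a partial safeguard, although the knees are not covered.

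Finally, one might suppose that early termination offers another QMT. Neither the bed-frame row of protocol Table 2 nor SAP 3.4.8 shows one.

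**Conclusion.** The point holds in a bounded form. Followed as written, the code yields a change score over different muscle sets whenever a test is missing at baseline or Week 60, and no other rule in the protocol or SAP prevents it. That much is certain from the code.

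The size and direction are conditional. The single-subject rises of 3.6, 6.3 and 8.3 points rest on the assumed 60% and 10% of predicted and on the weak muscle being left blank. They are enough to reverse the sign of one subject's result, but only to dilute a group mean unless several subjects are affected. With no missing test, or with untestable muscles entered as 0, the false rise does not occur.

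The consequence is limited. Protocol 2.3 and SAP 2.4 plan no formal testing, strength is exploratory, and the listed strength endpoint is manual dynamometry rather than bed-frame QMT. The correction is worth making because it is cheap and because the study is meant to guide further development.

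**What to change.** In SAP 3.4.8 and Appendix 9:

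1. For each subject and visit, keep only tests with a value at both baseline and that visit. Average both visits over that same set before taking the change, for the overall, upper and lower scores.
2. Report the number of tests contributing to each composite.
3. State that a muscle attempted but too weak to register is scored 0, and that tests missing for other reasons stay missing. Alternatively, present the zero-scored version as a sensitivity analysis. This step is needed because matching alone drops the lost muscle's own decline: in the 60%/10% example the matched change is 0, whereas the zero score gives −10/14 = −0.71 overall, −10/8 = −1.25 upper and −10/6 = −1.67 lower.
4. State the formula for the hand-held combined totals and apply the same matched-test rule to them.

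The cost is a few lines of code. Baseline values in the change table may then rest on fewer tests than those in the stand-alone baseline table, which a footnote can explain. The zero score also requires that the reason for a missing test was recorded; the documents do not say whether it was.

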## APPENDIX 10: QMT EXTREMITIES

**For Upper \_Extremity estimated from (SA, EF, EE, HG) :**

**SA (Shoulder Abduction)**

**69** salmvict Num 8 BEST12. BEST32. SAR (Shoulder Abduction-Left) QMT (kg)  
**70** sarmvict Num 8 BEST32. SAR (Shoulder Abduction-Right) QMT (kg)

**EF(Elbow Flexion)**

**58** eflmvict Num 8 BEST12. BEST32. EFL((Elbow Flexion-Left) QMT (kg)  
**68** efrmvict Num 8 BEST12. BEST32. EFR (Elbow Flexion-Right) QMT (kg)

**EE (Elbow Extension)**

**59** eermvict Num 8 BEST12. BEST32. EER (Elbow Extension-Right) QMT (kg)  
**60** eelmvict Num 8 BEST12. BEST32. EEL (Elbow Extension-Left) QMT (kg)

**HG(Hand Grip):**

55 hglmvict Num 8 BEST12. BEST32. HGL (Hand Grip-Left) QMT (kg)  
**56** hgrmvict Num 8 BEST12. BEST32. HGR (Hand Grip-Right) QMT (kg)

---

**For lower Extremity: estimated from (AD, KF, KE):**

**AD(Angle Dorsiflexors)**

**61** adrmvict Num 8 BEST12. BEST32. ADR (Ankle Dorsiflexors-Right) QMT (kg)  
**62** adlmvict Num 8 BEST12. BEST32. ADL (Ankle Dorsiflexors-Left) QMT (kg)

**KF (Knee Flexion)**

**65** kfrmvict Num 8 BEST12. BEST32. KFR (Knee Flexion-Right) QMT (kg)  
**66** kfimvict Num 8 BEST12. BEST32. KFL (Knee Flexion-Left) QMT (kg)

**KE (Knee Extension)**

**57** kelmvict Num 8 BEST12. BEST32. KEL (Knee Extension-Left) QMT (kg)  
**67** kermvict Num 8 BEST12. BEST32. KER (Knee Extension-Right) QMT (kg)

---

**Over all QMT is estimated from ( SA, EF, EE, AD,KF,KE,HG):**

**HG(Hand Grip):**

55 hglmvict Num 8 BEST12. BEST32. HGL (Hand Grip-Left) QMT (kg)  
**56** hgrmvict Num 8 BEST12. BEST32. HGR (Hand Grip-Right) QMT (kg)

**KE (Knee Extension)**

**57** kelmvict Num 8 BEST12. BEST32. KEL (Knee Extension-Left) QMT (kg)  
**67** kermvict Num 8 BEST12. BEST32. KER (Knee Extension-Right) QMT (kg)

**EF**(Elbow Flexion)

**58** eflmvict Num 8 BEST12. BEST32. EFL((Elbow Flexion-Left) QMT (kg)

**68** efrmvict Num 8 BEST12. BEST32. EFR (Elbow Flexion-Right) QMT (kg)

**EE** (Elbow Extension)

**59** eermvict Num 8 BEST12. BEST32. EER (Elbow Extension-Right) QMT (kg)

**60** eelmvict Num 8 BEST12. BEST32. EEL (Elbow Extension-Left) QMT (kg)

**AD**(Ankle Dorsiflexors)

**61** adrmvict Num 8 BEST12. BEST32. ADR (Ankle Dorsiflexors-Right) QMT (kg)

**62** adlmvict Num 8 BEST12. BEST32. ADL (Ankle Dorsiflexors-Left) QMT (kg)

**KF** (Knee Flexion)

**65** kfrmvict Num 8 BEST12. BEST32. KFR (Knee Flexion-Right) QMT (kg)

**66** kflmvict Num 8 BEST12. BEST32. KFL (Knee Flexion-Left) QMT (kg)

**SA** (Shoulder Abduction)

**69** salmvict Num 8 BEST12. BEST32. SAR (Shoulder Abduction-Left) QMT (kg)

**70** sarmvict Num 8 BEST32. SAR (Shoulder Abduction-Right) QMT (kg)

---

## APPENDIX 11: MMT SCORE MAPPING

Raw MMT scores will be mapped as follows:

‘0’ = 0

‘1’ = 1

‘2-‘ = 1.67

‘2’ = 2

‘2+’ = 2.33

‘3-‘ = 2.67

‘3’ = 3

‘3+’ = 3.33

‘4-‘ = 3.67

‘4’ = 4

‘4+’ = 4.33

‘5-‘ = 4.67

‘5’ = 5
